## Report

The project manager reports any changes in the status of participants in the “participants status” form of the RedCap project. The report in the form includes documenting:

- whether the withdrawal of the participant resulted from a decision by the participant or by the investigator (exclusion), and the reasons for the withdrawal, if known.
- whether the withdrawal was from all components of the research study or just the primary interventional component (assessment only).
- Note all communications and documentation in the notes section of the form, make sure it is complete, accurate, and contains all pertinent dates relating to events that resulted in the withdrawal of the participant, especially the date of withdrawal from your research study.

## Participant status definitions

Status	Definition	Report
Withdraw	
When a participant decides to withdraw from all components of a research study. The study's Manager must discontinue research activities involving the participant's participation such as:
 

• Interacting or intervening with the participant in order to obtain data about for the research study.

• Obtaining tracking data from FitBit, mLife app must be inactivated.

	
Complete the form immediately.
 
Inactivate mLife account
 
Highlight participant ID in the ASA24 accounts file.

Excluded	
When a participant reports a change in their health status or if an exclusion criterion becomes apparent, the study's manager must discontinue any research activities involving the participant. The participant should be informed of this decision promptly.
 
Examples of exclusion criteria that may arise after randomization include pregnancy, the decision to take weight loss medication, or the onset of a major health condition that prevents the participant from complying with the intervention.
 
Participants are made aware of these criteria at the orientation and training meetings to prevent any misunderstandings or disruptions during the study.
	
Complete the form immediately.
 
Inactivate mLife account
 
Highlight participant ID in the ASA24 accounts file.

Assessment only	
Sometimes, a participant may wish to withdraw from the primary interventional component of the study but is still willing to participate in other research activities that are outlined in the IRB-approved protocol and informed consent document. In such cases, these participants will only be contacted for data collection at the follow-up assessments.
	
Complete the form immediately.
 
Highlight participant ID in the ASA24 accounts file as "AO".
 
Turn text and notifications from the APP off.

Lost to follow-up	
Reported at the end of the trial for each of the assessments. Participants who were enrolled in the trial but are unavailable during follow-up assessments.
	
Complete the form after incentives distribution.
 
Inactivate mLife account (do not remove the link to FitBit)

Completed the study	Reported at the end of the trial: Participants who completed the 12-month assessment with a body weight report. Individuals who participated in the 12-month assessment but did not have an objective report of their body weight were determined as “Assessment Incomplete”.	Complete the form after incentives distribution. Inactive mLife account (do not remove the link to FitBit)
---------------------	---	---

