## Body-weight

Body weight is determined objectively and self-reported, with units for assessment reported in pounds (lb). The self-reported body weight is one of the first questions in the “health status” survey.

For the objective measure, participants receive instructions on how to use the provided Fitbit Aria Air scale, which syncs data to the Fitbit app. If the scale does not properly sync to their Fitbit app, participants are asked to take a picture of the scale's display and upload it to the instrument for data verification (self-reported, verified).

At the beginning of the trial, the first synchronized body weight reading is recorded as baseline. The body weight at 6 months and 12 months is determined as the last reading at weeks 26 and 52, respectively. The objective measure of body weight data is extracted from Fitbit and is pulled to the mLife site, from where it is exported to a CSV file. The body weight and date are then imported to RedCap at the assessment event using the “Body Weight (Fitbit)” instrument. Importing the body weight data marks the instrument as “complete,” so it

is not requested again from the participant. However, if no body weight data is reported for a participant at the end of the assessment period, they receive a link to either report their body weight directly to the form “Body Weight (Fitbit)” or to manually enter it into their Fitbit profile. In either case, they are prompted to upload a picture of the scale.

Participants follow the instructions below to get their body weight reading. These instructions are included in the RedCap instrument for the participant.

- Use Aria Air while barefoot.
- Make sure your feet are dry before weighing yourself.
- Place Aria Air on a hard, flat surface during use.
- Balance your weight evenly between both feet when you stand on the scale.
- Weigh yourself at the same time each day to see consistent trends. Your weight naturally varies over the course of the day.

---

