### **Sample size according to F-test**

Because our main outcomes will be measured at 12 months, we are using pilot work that collected weight loss outcomes at one year. Based on our pilot data (NETworks trial as this provides 12-month outcomes for weight), as well as several other one-year mHealth intervention studies, we calculated the sample size necessary to achieve 95% power (alpha = 0.05) for Aim 1 assuming a small effect size (Cohen's  $d = 0.1$ ) and an intra-cluster correlation (ICC) equal to 0.7. The sample size estimate was 200. For this calculation, we used an F-test on the interaction between time (two levels) and treatment arm (two levels) in a two-way ANOVA with repeated measurements (RM-ANOVA). We used a more conservative value of the ICC as compared to the actual estimate from the NETworks trial data (ICC = 0.9), as the latter would have resulted in a much smaller sample size (for a larger ICC, the residual sum of squares decreases, therefore precision increases and sample size decreases. The opposite is true when the test is strictly between subjects). Further, we assumed an attrition rate between 15 and 20%, and increased the sample size to 240. Thus, we aim to recruit a total of 240 participants (~120 per cohort), with the initial randomization assigning 120 to SocialPOD+points and 120 to SocialPOD-points.

Based on pilot study for overall app usage (Social POD  $50.7 \pm 25.0$  days and standard  $34.4 \pm 25.8$  days out of a possible 84 days) and points earned (mean of  $202 \pm 105$  points/participant with estimated 50 point difference between groups), our power for Aim 2 will be 99% for app usage and 95% for points earned based on our sample size from Aim 1.

We plan to use a random-effects (RE) model which is mathematically equivalent to repeated-measures-ANOVA. However, in the presence of loss to follow-up, RE models can handle responses that are missing at random. RE models can be adjusted for additional covariates if needed (though the randomization procedure should make this unnecessary). RE models provide additional information about the variance of the random effects which is valuable for understanding heterogeneity of responses and assessing the intra-cluster correlation (ICC).

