### **III. Below describes our plans for interim and final analyses and methods for handling missing data:**

#### ***Aims 1 and 2***

Data from all study measures will undergo initial data cleaning to identify potential outliers, determine distributions of variables, assess normality, and enumerate loss to follow-up and other missing data. Descriptive statistics at baseline will be compared between treatment groups to evaluate the success of randomization. ***Analyzing changes in weight between groups at year one***

***(Primary Aims 1):*** For Aim 1, the two levels of the treatment effect will be assignment to SocialPOD+points vs. SocialPOD-points, and the entire study sample will be included. Primary Aim 1 will be addressed using a repeated-measures mixed model with maximum likelihood estimation as provided by PROC MIXED in the SAS® system. Under the assumption that missing data are missing at random, mixed models provide unbiased estimates. These will be adjusted using robust computation of standard errors if non-normality is detected. These models will be estimated applying an intent-to-treat principle. Models for each primary aim are of the same form, with the difference of the groups being compared. Models will examine weight at baseline and at 12 months with a two-level time effect, two-level treatment effect, and two-way interaction between time and treatment. The repeated-measures model will contain time, treatment, time-by-treatment interactions, and any covariates associated with weight loss. Models will be adjusted for changes in PA (via

accelerometers). If the time-by-treatment interaction in a model is significant at the 0.05 level, this will be interpreted as a significant weight-loss effect for one treatment relative to the other.

**Analyzing differences in social support provision and receipt between groups (Aim 2):** For Aim 2, the model will regress support provided (total points earned) and social support received (mean of ratings of support provided to the individual over the 12 months) on treatment group, adjusted for the same covariates used in Aim 1.

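### Randomised participants given Excluded status lose their 12-month weight, and the primary model neither uses their post-baseline weights nor tests its missing-at-random assumption

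*Combined protocol and SAP*

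**What the plan says.** **Stopping data collection.** In the table under Participant status definitions, the Excluded row says the manager "must discontinue any research activities involving the participant" and that the mLife account is inactivated. The row covers events after randomisation. Its examples are pregnancy, "the decision to take weight loss medication", and a major health condition that prevents compliance. The Assessment only row keeps follow-up: "these participants will only be contacted for data collection at the follow-up assessments". The rows for loss to follow-up and for completion tell staff to leave the Fitbit link in place; the Excluded row does not.

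**Weight.** Under Body-weight, "The objective measure of body weight data is extracted from Fitbit and is pulled to the mLife site". If no reading arrives, the participant is sent a REDCap form or asked to enter the weight in Fitbit, with a photograph of the scale. Weights are also due at 6 months (Assessments table; Body-weight), and participants are asked to weigh themselves daily (Body weight tracking).

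**Analysis.** Part III of the Analysis Plan includes all participants in Aim 1 and states: "These models will be estimated applying an intent-to-treat principle". On the time points: "Models will examine weight at baseline and at 12 months with a two-level time effect". On missing data: "Under the assumption that missing data are missing at random, mixed models provide unbiased estimates". The section Sample size according to F-test adds that "in the presence of loss to follow-up, RE models can handle responses that are missing at random". The Aim 1 model is also adjusted for change in physical activity (PA). The bias table (part IV) and the section on biological variables (part V) say that medication will be controlled for.

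**The concern.** The protocol itself creates this missingness, and the triggers are plausibly tied to weight. Someone who decides to take weight loss medication may have been losing little and may later lose a lot; a major illness can move weight either way. Missing at random given baseline weight alone is therefore doubtful for this group.

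Four gaps follow. The two-time model ignores the post-baseline weights that would make the assumption more credible. No sensitivity analysis shows what happens if it fails. The documents do not say whether the target for someone who starts medication is the weight actually reached or the weight without medication. And an excluded participant has no 12-month PA, so adjusting for change in PA may drop the whole record, baseline included.

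At stake is whether a reader can tell how far the Aim 1 contrast depends on people whom the study stopped measuring.

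**Working it through.** **1. Does the rule end weight collection?** The Excluded row does not name weight, whereas the Withdraw row expressly stops Fitbit data. Inactivating the account closes the route through the mLife site but not the REDCap fallback. Requesting a weight through REDCap is, however, itself a research activity, so the general wording has the effect. No other section restores collection for this group.

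**2. The plan's own figure.** The stated inputs are two times, correlation 0.7, alpha 0.05 and effect 0.1. With 0.1 read as Cohen's f, lambda = N × 0.01 × 2 / 0.3. This gives 95.3% power at N = 200, so the plan's figure reproduces. (It does so only as f, although the plan labels it d; that is a separate matter.) Power is 95.6% with 204 measured, 94.5% with 192 and 93.1% with 180. Loss of power is not the issue.

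**3. Size of a possible shift.** The documents give neither an exclusion rate nor an SD of weight change, so these inputs are assumptions. Let p0 and p1 be the proportions excluded in mLife and mLife+points. Let D0 and D1 be the mean 12-month change of excluded minus remaining participants in each arm. If excluded participants are in effect represented by the rest of their arm, then

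shift in (mLife+points minus mLife) = p0 × D0 − p1 × D1.

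- 8% v 3% (about 10 and 4 of 120), D = 4 kg in both arms: 0.32 − 0.12 = 0.20 kg.
- The same with D = 8 kg: 0.64 − 0.24 = 0.40 kg.
- D = −4 or −8 kg: −0.20 or −0.40 kg.
- 5% v 5%, equal D: 0.
- 5% v 5%, D0 = 4, D1 = 0: 0.20 kg.
- 5% v 4%, D = 4 kg: 0.20 − 0.16 = 0.04 kg.
- Extreme case, 10% v 0%, D0 = 8 kg: 0.80 kg.

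With an assumed SD of change of 6 kg and 100 measured per arm, SE = 6 × √(2/100) = 0.849 kg. Shifts of 0.20, 0.40 and 0.80 kg are then 0.24, 0.47 and 0.94 SE. Coverage of a nominal 95% interval, 1 − P(|Z + r| > 1.96) with r the shift in SEs, is 94.4% at r = 0.236 and 92.4% at r = 0.471. For SDs of 5 to 8 kg, the ratios for 0.20 and 0.40 kg run from 0.28 and 0.57 down to 0.18 and 0.35. For scale, the three-month pilot difference quoted in the synopsis was 5.3 − 2.2 = 3.1 kg, against a different comparator.

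**4. What the 6-month weight would recover.** A simulation assumed baseline SD 18 kg; change SDs 4, 5, 5.5 and 6 kg at months 3, 6, 9 and 12; correlation 0.9 per three months; 8% v 3% excluded; and log-odds of exclusion rising 0.3 per kg of smaller loss. Bias of the two-time model, then with the 6-month weight added:

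- all exclusions at month 6: 0.29, then 0.00 kg;
- all at month 9: 0.34, then 0.07 kg (79% removed);
- half at month 3, half at month 9: 0.30, then 0.16 kg (about half removed);
- all at month 3: 0.22, then 0.22 kg (none removed).

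Complete removal at month 6 holds by construction, because exclusion there depends only on the weight that is then added. The assumed slope also makes excluded participants about 4.7 to 7.8 kg worse at 12 months than others in their arm, which is a strong setting. The comparison contains no PA covariate. It shows that the 6-month weight helps but is not enough for early exclusions.

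**The case against.** **The assumption is declared, and a two-time model matches the 12-month aim and the power calculation.** Both are true. A reader might infer that the exclusion rule flatly contradicts the intent-to-treat statement. The documents do not support that: a mixed model can include everyone randomised, under an assumption the plan states openly. What is missing is any test of that assumption.

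**Earlier weights are not all ignored.** Correct. Baseline weight is in the model; only weights between baseline and exclusion are unused.

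**Medication is to be controlled for.** Adjustment for medication cannot replace a 12-month weight that was never collected, and it does not define the estimand.

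**The arms differ only in points, so exclusions should be similar.** This stands as a reason to expect a small effect. Nothing in the documents suggests that medication starts or illness would differ nearly threefold by arm. With 5% v 4% and 4 kg, the shift is 0.05 SE and coverage 94.97%.

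**Dropout reporting is largely planned.** This also stands. The Report section requires reasons and dates, the Assessments table lists differential dropout, and part III will count losses. Reporting exclusions by arm, reason and date mainly makes that explicit.

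**Conclusion.** The concern holds as a gap in handling. Applied as written, the Excluded rule removes the 12-month weight of some randomised participants after events plausibly related to weight. The primary model then relies on missing at random given baseline alone, and the available text contains neither a sensitivity analysis nor an estimand for these events. Adjustment for change in PA may widen the gap by dropping their records.

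The size is unknown and may be nil. Under the assumed 8% v 3% imbalance, 4 to 8 kg departure and 6 kg SD, it is about 0.2 to 0.4 kg (0.24 to 0.47 SE). It approaches one SE only in extreme cases. A reader might infer that the result favours one arm; the documents do not support this, because excluded participants could end heavier or lighter than the rest of their arm and no rates by arm are given. This is a cheap improvement that should be made, not a demonstrated error in the result.

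**What to change.** Reconcile Participant status definitions with part III of the Analysis Plan, without changing any rule for ending the intervention.

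1. **If follow-up is over.** This is likely: cohort 2 training was in July 2023 and the intervention lasts 12 months, although the documents do not confirm closure.
   - Add the 6-month weight and available pre-exclusion Fitbit weights to the repeated-measures model or to an imputation.
   - Fit the primary model without change in PA, or impute PA, so that excluded participants stay in.
   - State the estimand for exclusions due to medication, health condition and pregnancy, handling pregnancy separately.
   - Add one delta-adjusted or tipping-point analysis that varies excluded participants' 12-month weight separately by arm in both directions, for example −8 to +8 kg. With 5% v 5% excluded, that grid spans −0.80 to +0.80 kg in the contrast; with 8% v 3%, −0.88 to +0.88 kg.
   - Fix all this before the statistician is unblinded, or label it post hoc.
2. **If any follow-up is open.** Let willing participants excluded for medication or a health condition move to the existing Assessment only status, so that weight is still collected. Analyse by assigned arm, with a supportive analysis that sets weights after medication start to missing.
3. **In either case,** report exclusions by arm, reason and date from the records already required.

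Cost: in the first case, analysis and reporting work on data already collected. In the second, a short protocol and IRB wording change and a few remote weight requests on scales participants already have. The downside there is that weights after medication start may dilute the contrast, which the supportive analysis addresses.

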## Training Session

This online training meeting launches the mLife intervention, equipping participants with skills to access and use the mLife app. Participants learn their group (mLife or mLife+), download the app, and link their Fitbit profile. Within the app, they edit their first name to match their preferred username, keeping their last name and email unchanged. Other participants' usernames display their chosen first name and the initial of their last name. Last names are not displayed for privacy. Sessions are limited to 1.5 hours.

### Schedule per cohort

#### Cohort 1, June 2022

June 28, 10:30 – 12:00M (Control group); 5:30 - 7:00PM (mLife+points group)  
June 29, 10:30 – 12:00M (mLife+points group); 5:30 - 7:00PM (Control group)  
June 30, 5:30 - 7:00PM (mLife+points group); 7:30 - 9:00PM (Control group) (makeup sessions)

#### Cohort 2, July 2023

July 5, 10:30 – 12:00M (Control group); 5:30 - 7:00PM (mLife+points group)  
July 6, 10:30 – 12:00M (mLife+points group); 5:30 - 7:00PM (Control group)  
July 7, 10:30 - 12:00M; 5:30 - 7:00PM (mLife+points group); 7:30 - 9:00PM (Control group) (makeup sessions)

## Prior to training meeting procedures

1. All of the participant's mLife accounts are created in a bulk upon completion of the randomization process.
2. Signup genius is setup to invite participants for the training meeting. Two signup are required as the training meeting are different per group (social support gamification).
3. Participants are contacted via automatic email sent from RedCap on the day they are randomized and accounts in the mLife application are created. The message includes the notification of the welcome to the study package shipping and the link to SignUp- Genius for the participant to book the training meeting.
4. Approximately 1h prior to each session, an activation link to the mLife account will be sent from the mLife staff site. A database with the list of the participants scheduled per session will be shared in OneDrive (training meeting materials folder). It will be used for preparation and attendance purposes.
5. An attendance form for the training session is included in the longitudinal project in RedCap for each cohort (training event).

## Training Meeting Agenda & Notes for Study Personnel

1. Only participants who have completed ALL components of the assessment are confirmed to attend the training meeting.
2. Training meetings are conducted LIVE; the recording of screenshots and in-app tasks are used to conduct and time the meeting.
3. The Principal Investigator opens up the session with a welcome back message and introduces the mLife team.
4. Demo (live + screenshots) of activation of mLife account and link of Fitbit - participants to complete a task in-app (15 min).
5. Q/A in breakout rooms. A staff member will be assigned to each group. At this point, participants will be allowed to share their screen.
6. Demo of intervention components (live + screenshots of mLife app with comments related to the explanations) - include explanations of the graphs for self-monitoring (PA, BW, and Kcals), emphasis on the definitions and importance of each.
7. Demo of diet logging (tutorial video). Participants complete one item/meal log. Reminder set as a text message at 8 p.m. (participants' time zone) (10 min)
8. Demo of tips of the day and podcasts access (live + screenshots). Participants "read" the available tip of the day. The first podcast should be available for them to listen to and mark as listened.
9. Demo of Social support activities (tutorial video). Demo of outreach message. Participants write their first request for support and/or rate a response. They like someone's PA, diet logging, or BW. For the control group, review the checklist. For the +Points group, review the points system and leaderboard, emphasizing its importance in weight loss.
10. Q/A in breakout rooms. A staff member will be assigned to each group. At this point, participants will be allowed to share their screen.
11. Key items and dates. A journey

### Notes:

- At the end of the meeting, ALL attendees must have their mLife account active and Fitbit devices synchronized to our site. A staff member will track this procedure via the mLife staff site.
- Tutorial videos for each section of the app with a feedback survey (within the RedCap project / training session event) will be shared with the participants via e-mail immediately after their meeting.
- Three days after the training meeting, a handout with recommendations for physical activity and caloric intake limit will be sent to each participant via email. The cutoff points on baseline body weight for caloric intake limit (handout) are: 1500 kcal/day for participants weighing  $\leq$ 248 lbs; 1800 kcal/day for participants weighing  $\geq$  249 lbs.

